4.3 Removal of Subjects from Therapy or Assessment

Subjects are free to withdraw consent and discontinue participation in the study at any time, without prejudice to further treatment. Subjects who discontinue prior to day 28 will be replaced.

A subject's participation in the study may be discontinued at any time at the discretion of the investigator. The following are reasons that may lead to a subject's discontinuation:

1. Subject develops intolerable adverse effects.
2. Subjects who experience a >60 msec prolongation of QTc interval or absolute QTc >500 msec (or >550 msec in the presence of a bundle branch block or paced ventricular rhythm) will be discontinued from treatment and followed by ECG until the QTc returns to baseline levels. Other abnormal findings on the ECG should be carefully considered and any subject excluded who, in the judgment of the PI, may not safely complete treatment in this study will be terminated from participation.
3. The subject is grossly non-compliant defined as:
 - a. Uncooperative/noncompliant and will not adhere to study responsibilities, including failure to appear at two consecutive visits.

- b. Taking prohibited medications as described in [Section 5.7.1](#), pending evaluation by the Sponsor.
- 4. The subject's health would be jeopardized by continued participation.
- 5. In the opinion of the Investigator, it is in the best interest to discontinue subject from study.
- 6. The subject wishes to withdraw for any reason.
- 7. The Sponsor elects to end the study, or any portion thereof, for any reason.
- 8. Any other safety results or adverse experiences that, in the opinion of the investigator, raise concerns about the safety or tolerability of VK5211.

Although a subject will not be obliged to give his/her reason for withdrawing prematurely, the Investigator will make a reasonable effort to obtain the reason while fully respecting the subject's rights. All subjects who are randomized and treated (i.e., received any amount of study drug) will be included in the safety analyses. Thus, every effort will be made to contact any subject who fails to attend any follow-up appointments/contacts, in order to ensure that he/she is in satisfactory health.

If a subject withdraws from the study as a result of meeting discontinuation criteria after the start of study drug administration, all post-treatment evaluations must be completed.

5 STUDY TREATMENT

5.1 Identity of Investigational Product

Viking Therapeutics will provide a supply of VK5211 in 0.5 mg, 1.0 mg, and 2.0 mg capsules plus matching placebo.

5.2 Treatment Quantity, Schedule and Form of Administration

Subjects will be provided with 1 bottle of VK5211 or placebo containing 30 capsules at Randomization. The clinical site will dispense one bottle at Randomization, Visit 2, and Visit 3. At each Visit, the previous bottle will be returned by the Subject and either re-dispensed to the subject or retained at the site until further notice from the Sponsor.

Subjects will be provided with a diary card at Randomization and Visit 3 and instructed to record times of dosing administration and meals and snacks beginning three days prior to Visits 2 and 4. The Investigator or designee will record this information on the eCRF.

5.3 Dose Justification

Dose selection for this Phase IIa efficacy, safety and tolerability study in subjects recovering from acute hip fracture is intended to establish the optimal dose for further development. Doses were selected based on study design and expected efficacy, safety, and tolerability.

In a 21-day Phase I study of VK5211 a trend toward increased lean body mass, as measured by Dual Energy X-ray Absorptiometry (DXA), was observed and was considered statistically significant at 1 mg VK5211, with no apparent change in fat body mass. Pharmacodynamic activity was also observed with dose-dependent changes for various hormones and lipids tested.

Dose-dependent decreases from baseline were noted for total testosterone and SHBG, while decreases from baseline for free testosterone were only observed at 1 mg of VK5211. Upon discontinuation of VK5211, serum total testosterone, free testosterone, and SHBG levels returned to (and were not significantly different than) baseline levels by Day 56. No apparent changes were noted for the FSH or LH. Dose-dependent changes were noted for HDL in the 0.3 mg and 1 mg groups, which also affected the total cholesterol to HDL ratio. No apparent changes were observed for the other lipid parameters tested: LDL, total cholesterol, and triglycerides. Therefore, testing a dose just above 1 mg (i.e. 2 mg) in this study will yield additional information on dose range effects. The placebo arm is included to fully assess safety and efficacy and to comply with Food and Drug Administration (FDA) guidance for New Drug Application (NDA) filing. Summarized below is the rationale for the doses selected in this study: 0.5 mg, 1 mg, and 2 mg/day of VK5211 capsules.

A total of 124 healthy male subjects have been enrolled across two completed Phase I clinical studies (48 subjects in Study V5211-01 [single dose study] and 76 subjects in Study V5211-02 [multi-dose study]). VK5211, administered orally in capsules, was safe and well tolerated by healthy male subjects up to the highest single dose tested (22 mg), and at daily doses of 0.1 mg, 0.3 mg, and 1 mg over a period of 21 days. No deaths or withdrawals due to adverse events (AEs) were reported. No subjects who received VK5211 had a serious adverse event (SAE); 1 subject who received placebo in Study V5211-02 had a SAE of Grade 3 cellulitis, which was considered unrelated to treatment. Of the 79 subjects who received at least one dose of VK5211 in the two Phase I studies, 40 subjects exhibited treatment-emergent adverse events (TEAEs). The most common TEAEs reported by two or more healthy male subjects were headache, procedural pain (only in subjects receiving muscle biopsies), dry mouth, and upper respiratory tract infection. Twelve subjects had TEAEs classified as study-drug related. The only treatment-related AEs occurring in more than one individual were dry mouth, acne, and increased LDL (2 subjects each). All TEAEs were mild or moderate in severity, and there were no premature study discontinuations due to an AE. All events were either transient or lasted for a few days and resolved before study termination. There was no dose-related trend in AEs. The changes from baseline in clinical laboratory parameters, vital signs, and ECG values were not graded as clinically important other than as mentioned above, and physical examination findings in all study subjects were not considered clinically significant.

The doses of 0.5 mg, 1 mg, and 2 mg/day of VK5211 over the 12-week study period in this Phase IIa study are likely to be well-tolerated based on the previous human data described above. These doses are expected to produce significant, clinically meaningful, and dose-dependent increases in lean body mass. These doses are also expected to enable an estimate of the minimal effective dose and possibly the dose needed to produce the maximal effect.

5.4 Labeling Information

Study subjects will receive an ID number to mask their identity.

Investigational products (IP) will be supplied to the study site in bottles containing 30 capsules. A single panel label on each container of IP will contain: protocol number, IP name, amount, randomization number, and instructions for use and storage (including temperature range). The following warning will also be included on the label “Caution: New Drug – Limited by Federal (or United States) law to investigational use.”

The Investigator agrees to neither dispense the study drug from, nor store it at any site other than the site listed on Form FDA 1572 or Investigator's Agreement. The Investigator agrees that the study drug will be dispensed by the Investigator or Sub-Investigator named on Form FDA 1572 or Investigator's Agreement, or qualified designees. The Investigator, Sub-Investigators, or qualified designees also agree that the trial drug will be dispensed only to study subjects who have provided written informed consent and have met all entry criteria. Clinical supplies may not be used for any purpose other than that stated in the protocol.

An adequate quantity of the study drug will be provided to replace units damaged in shipment/handling, to supply replacement subjects meeting the entry criteria.

5.5 Storage, Issue and Retention of Supplies

Viking Therapeutics, Inc. will provide all study treatment. Study treatment must be kept in an appropriate, secure area. All drug supplies are to be shipped under ambient conditions and stored at room temperature (between 15 - 25°C or 59 - 77°F), while at the clinical site. At the subject's home, the study treatment will be stored at ambient temperature. Excessive humidity should be avoided. Deviations from the established temperature, as well as the occurrence of excessive humidity, should be documented, and the sponsor should be notified.

The study treatment as supplied is considered study medication, which must be accounted for on the eCRF and in the paper drug accountability log at the time the medication is dispensed to the subject. Any unused portion should be returned to the clinic at each Visit or at the Early Termination Visit and should be recorded on the eCRF and in the paper drug accountability log.

The Principal Investigator will maintain an accurate record of the receipt of all study treatment as shipped by Sherpa Clinical Packaging on behalf of Viking Therapeutics, Inc., including the date received. In addition, an accurate drug disposition record will be kept, specifying the amount dispensed to each subject and the date of dispensation. This inventory record must be available for inspection at any time. Copies of this record will be provided to Viking Therapeutics, Inc. at the conclusion of the study.

Clinical supplies are to be used only in accordance with this protocol and under the supervision of the Principal Investigator.

After the study is completed, the Principal Investigator must account for all study treatment used, unused and partially used. After reconciliation, study treatment (used, unused, partially used) from each study site will be destroyed on site per site standard operating procedures. If a site has no specified procedure for the destruction of study treatment, it must be returned to Sherpa Clinical Packaging for possible analysis and final destruction.

5.6 Treatment and Protocol Compliance

5.6.1 Treatment and Protocol Compliance

At Screening, subjects who have been enrolled in the study as defined by signing the informed consent form will be assigned a subject number. The subject number will be a 5 digit number which will be assigned consecutively at the time the subject is screened (i.e. 2 digit site number plus 3 digit number for each subject screened, first subject screened will be 01-001, second

subject screened will be 02-002, etc...). The subject number will be used to identify the subject throughout the study.

Subjects who are randomized will receive a randomization number. The randomization number will be a 4 digit number that corresponds to the randomization schedule. The order in which treatments are received will be according to the randomization schedule.

Enrolled subjects who are not randomized, for whatever reason, will be discontinued from the study. Subjects who are randomized, but did not complete the study will also be discontinued from the study. Discontinued subjects will be included in the safety population or intent-to-treat population according to guidelines described in [Section 9.2](#).

5.6.2 Maintenance of Randomization Codes and Unblinding Procedures

A programmer not directly involved with the study will generate the randomization code. A sealed copy of the randomization scheme will be retained at the study site from the onset of the study and should be available to US FDA Investigators at the time of site inspection to allow for verification of the treatment identity for each subject, if requested. The randomization schedule will be available to the statistician after database lock.

Unblinding the study without the permission of Viking Therapeutics, Inc. is explicitly forbidden, except in the event of a **medical emergency** where the identity of the study treatment and dose must be known in order to properly treat the subject. Under these circumstances, the Investigator must contact the safety monitor or authorized designee for permission to unblind (See [Section 10.4.2](#)). The safety monitor or designee will verify the need and agree to unblind, retrieve the treatment code from the IWRS system, and provide the treatment information to the Investigator.

If the blind is broken, the safety monitor or authorized designee must document the date, time, and reason. A written report should be sent to Viking Therapeutics, Inc. within 1 working day.

Viking Therapeutics, Inc. may unblind the treatment assignment for any subject with an expedited SAE report. If the SAE requires that an expedited regulatory report be sent to one or more regulatory agencies, a copy of the report identifying the subject's treatment assignment may be sent to clinical investigators in accordance with local regulations and/or the policies of Viking Therapeutics, Inc.

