2 INVESTIGATIONAL PLAN

2.1 Overall Study Design and Plan: Description

This is a randomized, double-blind, parallel group, placebo-controlled, multi-center study to investigate the safety, tolerability, and efficacy of VK5211 after 12 weeks of treatment.

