10.5 Causality Assessment of Adverse Events

For all AEs, the Principal Investigator will provide an assessment of causal relationship to the IP. The causality assessment must be recorded on the appropriate AE reporting page of the subject's eCRF/Source Documents. Causal relationship will be classified according to the following criteria:

- **UNRELATED:** The event is definitely not associated with the study medication.
- **POSSIBLE:**
 - The event follows a reasonable temporal sequence from drug administration.
 - The event could have been produced by the subject's clinical state or by other modes of therapy administered to the subject.

- **PROBABLE:**
 - The event follows a reasonable temporal sequence from drug administration.
 - The event abates upon discontinuation of the drug.
 - The event cannot be reasonably explained by the subject's clinical condition or other therapy.
- **DEFINITE:**
 - The event follows a reasonable temporal sequence from drug administration.
 - The event abates upon discontinuation of the drug.
 - The event cannot be reasonably explained by the subject's clinical condition or other therapy.
 - The event occurs immediately following study drug administration, improves on stopping the study drug OR reappears on re-exposure.

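### Protocol Section 5.6.2 lets expedited SAE reports that name a subject's treatment reach clinical investigators on sponsor policy alone, with no clinical-need test

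*Protocol*

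**What the plan says.** Protocol Section 2.1 describes the trial in these terms: "This is a randomized, double-blind, parallel group, placebo-controlled, multi-center study". Section 5.6.2 then sets out how treatment codes may be released.

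The general rule is: "Unblinding the study without the permission of Viking Therapeutics, Inc. is explicitly forbidden, except in the event of a" medical emergency in which the subject cannot be treated properly unless the arm and dose are known. In that case the investigator asks the safety monitor or a designee, who checks the need, takes the code from the IWRS and passes it on.

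The last paragraph of the section adds a second route: "Viking Therapeutics, Inc. may unblind the treatment assignment for any subject with an expedited SAE report". It continues: "If the SAE requires that an expedited regulatory report be sent to one or more regulatory agencies", a copy of that report showing the subject's "treatment assignment may be sent to clinical investigators in accordance with local regulations and/or the policies of Viking Therapeutics, Inc".

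On the recipients' role, Section 10.5 states that for every AE "the Principal Investigator will provide an assessment of causal relationship to the IP".

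**The concern.** The second route can put one subject's arm in the hands of the people whose judgement the blind is meant to protect.

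- **Causality.** Investigators rate relatedness for all AEs (Protocol 10.5). AEs are summarized by relationship to study drug (Protocol 9.5.1, SAP 2.9.1), and the safety comparison with placebo is a secondary objective (Protocol 3.2).
- **Discontinuation.** An investigator may end a subject's participation at his or her discretion (Protocol 4.3).
- **Staff-administered measures.** Site staff run the 6MWT, grip strength and SPPB, and conduct the SF-36 and PADL/IADL interviews (Protocol 6.8, 6.9 and Appendix 15).

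An investigator who has learned an arm could be influenced in later decisions and ratings for that subject. A report that links an event to a named dose could also colour the rating of similar events in other subjects. Once made, the disclosure cannot be undone.

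**Working it through.** No formula applies. The point rests on no power, effect size or rate, so the check is to compare the two release routes in Section 5.6.2 and then look for a limit elsewhere.

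**1. The two routes compared**

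| | Emergency route | Expedited-report route |
|---|---|---|
| Who decides | Safety monitor or designee, at the investigator's request | Sponsor, at its discretion; the sponsor or its designee also determines which SAEs are expedited (10.4.2) |
| Test | Arm and dose needed to treat the subject | None beyond expedited status, plus local regulations and/or sponsor policy |
| Recipient | The investigator who asked | Clinical investigators; the subject's own site is not excluded |
| Blinded version | Not applicable | Not provided for |
| Record | Date, time and reason; written report to the sponsor within 1 working day | None stated for this route |

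The documentation rule stands between the two routes. It names the safety monitor or designee as the one who records and the sponsor as the one who is told. It therefore fits the emergency route, and it is not clear that it reaches disclosures the sponsor makes itself.

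**2. What the and/or does.** If a local regulation required the disclosure, the first ground would suffice. The added alternative lets sponsor policy carry the disclosure where no regulation asks for it. That policy is not in the documents.

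**3. Is there a limit elsewhere?** The SAE provisions (Protocol 10.3 to 10.5) and the SAP contain no need-to-know limit and no blinded copy for sites. SAP 2.11 points the other way in spirit: at the primary analysis, group results become known but individual assignments stay blinded.

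**4. Is there another unblinded reader?** Yes. The independent DMC receives unblinded results (Protocol 10.1) and is notified of SAEs (10.4.2). The documents give no reason why assessing investigators also need the arm.

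**5. Can the subject still be under assessment?** Yes, though not always. Subjects withdrawn under the discontinuation criteria must still complete post-treatment evaluations (Protocol 4.3), and follow-up runs to Day 168 (Table 1).

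**6. Which endpoints are exposed?** Later causality ratings and the exploratory tests and interviews are exposed. The DXA analysis takes central-reader values as primary (SAP 2.10.2.1), so knowledge at the site can hardly alter the measurement. The exposure is small rather than nil, because a decision to stop treatment can affect whether a scan meets the stringent 56-day definition in the same SAP section.

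**The case against.** The strongest case against the point is that the provision is narrow and optional. It says may twice, is triggered only by SAEs that need an expedited report to an agency, and reveals one subject at a time. Sponsor policy may already restrict such copies. All of this stands, and it limits the size of the point without removing the permission.

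The bias path is also shorter than it looks. The initial SAE form is due within 24 hours and must include the investigator's relatedness judgement (Protocol 10.4.2), so the triggering event is normally rated before any unblinded report exists. That stands for the first rating. The same section allows signed follow-up forms with corrections, so a rating can still change afterwards. The 6MWT, grip and SPPB instructions are scripted, and only standard encouragement is allowed in the 6MWT (Appendix 15.2 to 15.4). Scripts reduce assessor influence but do not abolish it. These tests are exploratory.

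Three stronger readings are tempting, and the documents do not support them:

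- *Section 5.6.2 contradicts itself.* It does not. The general rule is "Unblinding the study without the permission of Viking Therapeutics, Inc. is explicitly forbidden", and in the expedited route the sponsor is the party that acts.
- *Routine safety reporting breaks the double blind.* Ordinary AE and SAE reporting is outside the provision, and a permitted disclosure for single subjects is not a break of the trial's blind.
- *One revealed arm helps site staff to guess others.* This cannot be judged. The randomization details are in a separate plan (SAP 2.15), and neither document says how blocks, if any, are formed or whether they lie within a site.

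Finally, whether a change is fully compatible with 21 CFR 312.32, which Section 10.4.2 cites, cannot be checked from the documents. The fix must therefore leave room for disclosures that a regulation requires.

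**Conclusion.** The point holds as a minor one. Section 5.6.2 permits an avoidable, subject-level disclosure of treatment to investigators on sponsor policy alone. It carries none of the safeguards that the emergency route has.

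Its size cannot be given as a number. The documents state no expected count of expedited reports, and any percentage of subjects affected would be a guess. The exposure is limited to causality ratings and discontinuation decisions made after the disclosure, and to the staff-administered exploratory measures. The primary DXA result is little exposed.

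The conclusion assumes that no unseen sponsor policy already withholds the assignment from sites. If one does, the protocol should still say so, because its text currently permits the opposite.

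**What to change.** Reword the last paragraph of Protocol Section 5.6.2:

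- Remove sponsor policy as a sufficient ground for disclosure to investigators.
- State that copies of expedited reports sent to investigators carry no treatment assignment, unless a regulation requires it or the emergency route in the same section applies.
- State that unblinded versions go to the regulators and the DMC.
- Require that every disclosure of an assignment, by either route, is documented with date, time and reason.

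The emergency route stays as written, and so does any disclosure that a regulation demands. The cost is a blinded and an unblinded version of each report concerned, and investigators see less detail in the copies they receive. The design, sample size and analysis do not change.

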5.7 Concomitant Therapy

5.7.1 Allowable Medications and Therapies

As described in the inclusion/exclusion criteria, subjects will be permitted to stay on their stable dose(s) of blood pressure medication, diabetes medications (excluding insulin), and lipid-lowering medications. Medications such as antibody-based therapy (denosumab), parathyroid hormone, systemic estrogens or estrogen receptor modulators (SERMS) will not be permitted during the 3 month treatment period and 3 month follow up period. Bisphosphonates taken at the time of Screening may be continued unchanged throughout the 3 month treatment period and 3 month follow-up period. Hormonal therapy is not permitted during the trial. If a subject begins taken any of these medications, the subject may be discontinued from the study pending individual evaluation by the Sponsor. Vitamin D₃ and/or calcium supplements are permitted during the study. Other chronic medications will be permitted based on Investigator judgment and after consultation with the Sponsor's medical monitor.

